RESEARCH PROTOCOL

Version no.1; Date: 17th January 2018

Primary Investigator: [name] [name]

Co-investigators: [name] [name], [name] [name]

a) Title:

Glass ionomer sealant versus fluoride varnish application to prevent occlusal caries among preschool children - A randomized controlled trial.

b) Introduction:

Problems encountered in clinical work

Dental caries has been considered as a significant public health problem worldwide (Selwitz et al., 2007; Peterson 2005). Despite that its prevalence might have declined in many developed countries (Selwitz et al., 2007), epidemiological data have shown a considerable rise in global caries rate, posing a significant point of issue in public health (Bagramian et al., 2009; Peterson 2005).

In Hong Kong, the problem of dental caries among preschool children remains unsolved and the severity has exacerbated. The number of decayed, missing and filled teeth among pre-school children had increased from 2.3 in 2001 (Hong Kong Department of Health, 2002) to 2.5 in 2011 (Hong Kong Department of Health, 2012). The latest government oral health survey found that more than 50% of the preschool children had caries experience, with over 90% of the decayed teeth being untreated and that one in every 20 children had even developed dental abscesses from extensive carious teeth (Hong Kong Department of Health, 2012).

Preventing caries development in primary molars is especially important, as they would remain in the oral cavity for more than 10

years before exfoliation. Premature loss of primary molars can seriously affect the development of permanent dentition, including space loss and malocclusion. Moreover, second primary molars were reported to be the most susceptible to caries development at the 4 and 5-year-olds in studies conducted in different countries around the globe (Elfrink et al., 2006; Autio-Gold & Tomar, 2005; Holt, 1995, Holland & Crowley, 1982), with a predilection for their occlusal surfaces (Douglass et al., 1995; Bimstein et al., 1981). Pits and fissures on the occlusal surface of permanent molars are considered to favor biofilm formation and retention, which the rate of occlusal caries development and progression are comparatively higher than that of smooth surface caries (Batchelor et al., 2004; Brown, 1995). In primary second molars, the generally deeper pits and fissures, as well as the presence of buccal pits and palatal fissures at mandibular and maxillary second primary molars respectively, may also contribute to its caries prevalence (Bimstein 1981).

Incipient carious lesions occur when minerals from the enamel subsurface are being lost initially, which may progress to cavitated carious lesions requiring restorations if left untreated. Calcium and phosphate ions can be redeposited to demineralized enamel via the process of remineralization as crystal voids, enhancing the strength by creating a net mineral gain (Cochrane et al., 2010). Remineralization with appropriate agents has proven effective to treat incipient carious lesions (Mohd Said et al., 2017; Cochrane et al., 2010). The use of fluoride promotes the remineralization in incipient carious lesion. Fluoride facilitates adsorption of calcium ions to demineralized enamel surface, as well as substituting hydroxyl ions (OH⁻) to form fluorapatite, that have a strong acid resistance against demineralization (Featherstone, 1999).

Topical fluoride varnish (TFV) with 5% sodium fluoride in its content has proven effective in preventing caries among children and

adolescents (Marinho et al., 2009; Marinho et al., 2002). Its reduction in DMFT is well supported by Cochrane reviews and clinical trials (Ahovuo-Saloranta et al., 2016; Marinho et al., 2013). When the varnish containing high concentration of fluoride (22,600ppm) is applied to the tooth surface, it forms a fast-setting base that releases fluoride subsequently (Marinho et al., 2002). It also increases the retention of fluoride on tooth surface, allowing a continuous flow of fluoride ions to enamel, dentine, plaque and saliva (Mohd Said et al., 2017). However, its effect in preventing pit and fissure caries in primary dentition has not been assessed (Ahovuo-Saloranta et al., 2016).

The 5% sodium fluoride varnish containing 22,600 ppm fluoride is the only fluoride agent that is considered safe-to-use for children aged below 6 years (Maguire, 2014; Weyant et al., 2013; American Dental Association Council on Scientific Affairs, 2006). As the quantity of fluoride contained in a single application dose of 5% sodium fluoride varnish is relatively small (5.65mg in 0.25mL), it is well below the probable toxic dose (5mg/kg) (Lee, 2015). Comparing with fluoride gels or other fluoride agents, the potential risks associated with inadvertent ingestions in young children is also reduced (Weyant et al., 2013; American Dental Association Council on Scientific Affairs, 2006). The current recommended dosage of 5% sodium fluoride varnish for children between 2-5 years old is 0.25mL, applying at intervals of every 3-6 months, depending on the caries risk assessed (Lee, 2015; American Dental Association Council on Scientific Affairs, 2006).

Pit and fissure sealants have been a recommended procedure in preventing pit-and-fissure caries development in permanent molars. Both resin-based and glass-ionomer sealant serve as a physical barrier between enamel and the oral environment, reducing plaque retention by sealing occlusal pit and fissures (Nunn *et al.*, 2000). Multiple systematic reviews and clinical trials have concluded that

fissure sealants are significantly more effective than topical fluoride varnishes in preventing occlusal caries in permanent molars (Levy, 2012; Liu et al., 2012). However, a recent Cochrane review suggested that there was still insufficient evidence to determine superiority of resin or glass ionomer fissure sealants over topical fluoride varnishes for occlusal caries prevention, due to the lack of reliable results and low quality of evidence (Ahovuo-Saloranta et al., 2016).

Also, most studies were conducted on permanent first molars among school children (Ahovuo-Saloranta et al., 2016), whom cooperation and moisture control can be easily achieved. However, application of fissure sealants, especially resin-based sealant, in very young children can be a technique-sensitive procedure. Compared with a mean treatment time of less than 3 minutes for varnish application, application of resin-based sealants required over 15 minutes (Splieth et al., 2001). Moisture control is also of paramount importance for the retention and success of resin-based sealants (Gooch et al., 2009), which may be difficult among young preschool children.

Glass-ionomer sealants can chemically bond to enamel and are more tolerable to inadequate moisture control (Antonson et al., 2012). As its application requires less clinical steps, glass-ionomer sealant is comparatively more acceptable to younger patients and can be used in outreach settings with a large number of participants. The fluoride releasing ability is also beneficial in preventing caries especially at adjacent tooth surfaces (Cagetti et al., 2014). However, its retention rate is significantly lower than that of resin-based sealants (Antonson et al., 2012), its success rate in preventing fissure caries in very young patients is still unknown.

c) Aims and Hypotheses to be Tested:

Aims

To compare the efficacy of glass ionomer fissure sealant versus topical application of 5% sodium fluoride varnish in prevention of occlusal caries among preschool children.

Hypotheses to be tested

Greater reduction in occlusal caries in preschool children by glass ionomer fissure sealant compared to topical application of 5% sodium fluoride varnish.

d) Plan of Investigation:

(i) Subjects

The proposed study will be conducted in kindergartens in Hong Kong. The communal water supply in Hong Kong is fluoridated at a concentration of 0.5 ppm. Most child formula toothpastes available in Hong Kong contain fluoride at a concentration of 500–600 ppm. Generally healthy children aged between 3-4 years with no remarkable medical history will be invited to participate in this study. Children with at least one of the following criteria, deemed to be at moderate to high caries risk (American Academy of Paediatric Dentistry, 2013), will be included in this study:

Moderate risk	The child is a recent immigrant.
	The child has plaque on teeth.
High risk	The parent/ caregiver has low socioeconomic status.
	The child has >3 between meal sugar-containing snacks or beverages per day.
	The child is put to bed with a bottle containing natural or added sugar.
	The child has >1 decayed/missing/filled

	surfaces.
	The child has white spot lesions or enamel defects.
	The child has visible cavities or fillings.

They are thus qualified to receive fissure sealants and topical fluoride application regularly every 3 months (Lee, 2015; AAPD, 2013).

The following will be excluded from this study:

1. Children with the presence of caries of ICDAS code 3, 4, 5, or 6 on other primary teeth.
2. Children who had received professional fluoride application in the past 6 months.
3. Children with serious systemic disease or taking long term medication.
4. Children who are uncooperative or refuse the treatment.
5. Second primary molars that are (i) with caries in dentin indicated by ICDAS code 4, 5 or 6; (ii) partially erupted; (iii) with fillings and/or sealants; and (iv) hypoplastic or hypomineralized.

(ii) Methods

Sample size calculation

The primary outcome of this clinical trial is carious cavity development into dentin (ICDAS code 4,5 and 6) on occlusal surfaces of primary second molars. Sample size is calculated to be 256 children with a type I error of 0.05 and a power of 90%. This is based on the results of a previous study on primary molars (Honkala et al., 2015), where the real difference between fluoride varnish and sealant effect on occlusal caries reduction was 30%. Calculating with a 5% statistical significance level and a 90% power, a minimum of 102 children in each group will be required. To allow for loss of power due to drop-out, the initial sample size should be around 25%

larger, i.e. 128 children are needed in each group at the beginning of the study. Thus, the total initial sample size will be 256 (128 x 2 groups).

Ethical approval

Ethical approval will be obtained from the Institutional Review Board of the University of Hong Kong/Hospital Authority Hong Kong West Cluster and the trial will be registered in the HKU Clinical trials registry.

Recruitment and screening

Children studying in kindergarten 1 and Nursery 2 will be invited to participate in this proposed study. An invitation letter will be sent to their parents, explaining the objectives and procedures of the study. Only those children whose parents have signed the informed consent will be included in this study. Children will be screened for the following aspects:

1. Plaque assessment using visible plaque index (VPI) (Ainamo & Bay, 1975)
2. Overall tooth status with diagnostic criteria recommended by WHO in 2013, in the form of:

Classification	Description
Decay (d)	presence of dentin carious lesion(s) with or without a restoration.
Missing (m)	the tooth is extracted due to caries.
Filling (f)	presence of a temporary or permanent filling due to caries with no decay.

3. Dental caries status based on ICDAS code score (International Caries Detection and Assessment System Coordinating Committee, 2009; Ismail et al., 2007), which is summarized below:

Code	Classification	Description
0	Smooth & intact tooth surfaces	No evidence of dental caries or questionable changes in translucency of enamel after prolonged drying (around 5 seconds).
1	Visual change in enamel	Color changes due to caries which is not consistent with the clinical appearance of sound enamel, which is seen only after prolonged drying.
2	Distinct visual change	Cariou opacity (white spot lesion) and/or brown carious discoloration which is wider than the natural fissure/fossa that is not consistent with the clinical appearance of sound enamel, when seen wet and after drying.
3	Localized enamel breakdown due to caries with no visible dentin or underlying shadow	The tooth viewed wet might have a clear carious opacity and/or brown carious discoloration which is wider than the natural fissure/fossa that is not consistent with the clinical appearance of sound enamel.
4	Underlying dark shadow from dentin with or without localized enamel breakdown	The carious lesion appeared like a shadow of discolored dentin appeared through an apparently intact enamel, which might show signs of localized breakdown.
5	Distinct cavity with visible dentin	Cavitation in opaque or discolored enamel exposing the dentin beneath, involving less than half of the tooth

		surface.
6	Extensive distinct cavity with visible dentin	Cavitation in opaque or discolored enamel exposing the dentin beneath, involving at least half of the tooth surface. Obvious loss of tooth structure and dentin is clearly visible on the walls and at the base in a cavity that involved at least half of the tooth surface.

Questionnaire survey

Parents are required to complete a validated questionnaire before the baseline examination, which consists of the following sections:

- (1) The child's personal information - gender, age, place of birth, medical history of systemic disease and long term medication
- (2) The child's oral health-related behaviors – snacking habit, frequency of toothbrushing, parent's supervision in toothbrushing, use of toothpaste and night bottle habit
- (3) The child's dental history – past dental treatment received
- (4) The child's socio-economic background - parents' age, education level, household income and number of children

(iii) Study design

Clinical exam

Clinical examination will be carried with the child lying supine on table provided by the kindergarten.

The Visible Plaque Index (VPI) (Ainamo & Bay, 1975) will be used to measure the oral hygiene status of the child. Buccal and palatal/lingual surfaces of 6 index teeth (teeth 55, 51, 63, 71, 75, 83) will be examined. The presence or absence of visible plaque on the tooth surfaces mentioned above will be recorded as "1" or "0" respectively. The VPI score of the child will be obtained by dividing the number of

tooth surfaces recorded as “1” with the total number of tooth surfaces recorded as “0” and “1”, i.e.

$$\text{VPI} = \frac{\text{number of tooth surfaces recorded as “1”}}{\text{total number of tooth surfaces recorded as “0” and “1”}}$$

b. Tooth status

All tooth surfaces will be first wiped clean and dry by clean gauze and cotton swab for visual inspection of caries. A basic dental charting will be first performed, which the overall primary dentition will be further assessed and recorded based on the presence of decayed (d) missing (m), and filled (f) teeth, as recommended by the WHO in 2013.

Then the ball end of the CPI probes will be used to slide through the pits and fissures of primary molars to detect any enamel cavities or discontinuities. The status of the occlusal surfaces of primary molars will be recorded based on the ICDAS coding system (International Caries Detection and Assessment System Corrdinating Committee, 2009; Ismail et al., 2007).

Children who do not meet all the inclusion criteria will be given an examination report. Parents will be informed regarding the carious teeth and will be advised to seek treatment from private dental practitioners or specialist paediatric dentists promptly. Children with second primary molar(s) that fulfill all the criteria will be included in the study.

The occlusal fissures of each of the upper and lower molars included in the study will be assessed, and the fissure morphology (deep/shallow) and ICDAS score will be recorded.

Randomization and treatment allocation

By using the random numbers generated by stratified block randomization method in a personal computer, children will be randomly allocated to one of the two study groups:

(1) NaF varnish

— Application of a 5% NaF varnish (Duraphat, Colgate-Palmolive Ltd, Waltrop, Germany) on the occlusal surfaces of primary second molars and all other teeth, every 3 months during the study period;

(2) GI sealant

-- Glass ionomer sealant (GC Fuji VII® (pink)) on all primary second molars included in the studies, with no further repair/replacement of the sealant

Interventions

Immediately after the oral examination, a chair-side dental assistant will prepare the materials respective to the groups allocated on the random allocation list.

For the sealant group, glass ionomer sealants will be applied using the finger pressure technique described in the WHO manual for atraumatic restorative treatment (ART) (Frencken et al.; 1997). The primary second molars included in the study will first be cleaned and dried by wiping with gauze and cotton pellets. Following the manufacturer's instructions, further cleaning of the fissures will be performed by applying GC cavity conditioner with micro-applicator for 10-15 seconds, then clean with wet cotton pellets for several times. The surface will be dried with cotton pellets. The dental assistant will mix the glass ionomer sealants (GC Fuji VII) in a standardized proportion with an amalgamator. Glass ionomer sealants will be applied to the occlusal surface with blunt end of an applier and slightly overfilled. A gloved finger with petroleum jelly will be used to push and rub the materials into the pits and fissures, as well as removing the excess sealants from the tooth surfaces. The sealants will be covered and protected by a layer of petroleum jelly (Vaseline®).

In the NaF varnish groups, 0.25mL (one drop) of the varnish will be placed in a plastic dappen dish. A disposable microbrush will be used to apply the varnish onto the second primary molars included in the study and all other teeth. The child will be instructed not to eat or drink after the application of varnish for at least half an hour.

Follow-up evaluation

Children in the NaF varnish group will be recalled at the 3rd, 6th, 9th, 12th, 15th, 18th, 21st and 24th months for reapplication of fluoride varnish. Similar to baseline, 0.25mL (one drop) of the 5% sodium fluoride varnish will be applied using a disposable microbrush. At the 6th, 12th, 18th and 24th months, a clinical examination will be performed for all children in both groups. During the follow-up examination, overall VPI and dmft will be recorded. ICDAS score will be recorded for each primary second molar included in the study.

Sites with sealant will be evaluated in the following aspects:

Aspect	Code	Classification	Description
Retention	0	Fully intact	Sealants are fully intact without apparent loss of materials.
	1	Partial loss	Sealants are retained with partial loss
	2	Total loss	No sealant materials are found on tooth surface.
Caries	0	No caries	No caries found at the margin of the sealants.
	1	Presence of caries	Evidence of caries found at the margin of the restoration.

A 10% random sample will be re-examined during every examination to monitor intra-examiner reproducibility.

An oral health talk will be given to the parents of the participants. During the talk, the parents will be instructed to choose fluoridated toothpastes and child toothbrushes throughout the period of study. In case of any adverse event during the study, the parents will be advised to contact the principal investigator.

Outcome measures

The primary outcome measure is carious cavity development into dentin (ICDAS code 4, 5 and 6) on the occlusal surfaces of primary second molars over time.

Only one registered dentist will be the examiner in the kindergarten throughout the whole 24-month study period. She will receive training and calibration by epidemiologists before examining the subjects. The following dental equipment will be used:

- (1) Disposable dental mirror attached to a handle with light-emitting diode intra-oral illumination
- (2) World Health Organization CPI periodontal probe(405/WHO probe)

A 10% random sample will be re-examined during every examination to monitor intra-examiner reproducibility. The ICDAS score will be recorded based on the index proposed by Ismail et al., 2007.

Parents will be notified about the development of carious lesions. Advice on oral hygiene maintenance and seeking private dentists for respective dental treatments will be given to the parents in the form of a detailed report.

The proposed study will be a randomized controlled trial with 2 parallel groups. The unit of randomization will be each individual participant, but not each tooth of the mouth.

(iv) Data processing and analysis

Data analysis will be performed using SPSS® Statistics version 23.0 (SPSS Inc, Chicago, IL, USA). All children with missing data resulting from loss to follow-up or unrecorded data will be excluded from the analysis. Data proof-reading will be performed after data entry to identify and correct any errors before analyzing the data. An intention-to-treat analysis will be undertaken. Intra-examiner agreement in the diagnosis of dental caries will be assessed by Cohen's Kappa statistics.

Chi-square test will be used to assess the difference between groups according to the distribution of children's demographic characteristics such as gender, place of birth, oral health-related behavior, use of fluoride toothpaste, snacking habit, parents' education and family income.

The outcome measures are the mean change in the overall dmft scores and ICDAS code in primary second molars over time. Within-group comparison of changes in mean overall dmft scores and ICDAS scores at 24 months and mean change in overall dmft scores and ICDAS scores will be assessed by applying repeated analysis of variance (ANOVA) (or Friedman test for non-parametric data).

Student's t-test will be applied to differentiate the comparability between the treatment groups according to the subject's baseline conditions, including the child's age, dmft score and VPI score.

Since more than one molar will be included from one child, GLIMMIX procedure will be used to adjust for the clustering effect. The first level and second level will be the primary second molar and the subject

respectively. This analysis accounts for the correlation (clustering) between observations of multiple molars from the same child.

A multi-level logistic regression analysis will be performed to analyze the effects of independent variables on the ICDAS scores at the 6, 12, 18 and 24 month examinations. The independent variables included the child's demographic characteristics, oral health-related behaviors and clinical characteristics (gender, place of birth, frequency of tooth brushing, use of fluoride toothpaste, snacking habits, mother's education, father's education, family income, VPI score, dmft score and the treatment group). The level of statistical significance for all tests will be set 5%.

Key References:

3. American Academy of Pediatric Dentistry. Guideline on caries-risk assessment and management for infants, children, and adolescents. *Pediatr Dent.* 2013;35(5): E157-64.
4. American Dental Association Council on Scientific Affairs. Professionally applied topical fluoride: evidence-based clinical recommendations. *J Am Dent Assoc.* 2006;137(8): 1151-9.

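### The aim is prevention of occlusal caries, but study molars may already have enamel caries (ICDAS 1–3), and the pooled analysis cannot separate prevention in sound molars from arrest of existing lesions

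*Combined protocol and SAP*

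**What the plan says.** - **Aim.** Section c) sets out to compare sealant and varnish "in prevention of occlusal caries among preschool children". The hypothesis speaks of a greater reduction in occlusal caries with sealant. Neither is limited to dentin caries.
- **Molar eligibility.** Under d)(i) Subjects, exclusion 5 removes a study molar for caries only if it is "with caries in dentin indicated by ICDAS code 4, 5 or 6". Codes 0, 1, 2 and 3 remain eligible.
- **Child eligibility.** Exclusion 1 bars "Children with the presence of caries of ICDAS code 3, 4, 5, or 6 on other primary teeth". Code 3 is therefore a bar on other teeth but not on the study molar. One of the qualifying high-risk criteria is "The child has white spot lesions or enamel defects".
- **What the codes mean.** In the ICDAS table under d)(ii), code 1 is "Color changes due to caries which is not consistent with the clinical appearance of sound enamel", code 2 is a carious opacity or discoloration, and code 3 is "Localized enamel breakdown due to caries with no visible dentin or underlying shadow".
- **Primary outcome.** Under both Sample size calculation and Outcome measures, it is an occlusal dentin cavity, ICDAS 4–6, with no reference to the starting code.
- **Baseline data.** Under Tooth status in d)(iii), ICDAS and fissure morphology are recorded for each study molar. Randomization is by stratified blocks, but no stratification factor is named.
- **Analysis.** The covariates listed in d)(iv) for the multi-level logistic regression include plaque score, dmft and treatment group, but not baseline molar ICDAS or any interaction. The decayed component of dmft counts dentin lesions only, so it does not stand in for enamel lesions.

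**The concern.** By the protocol's own definitions, some enrolled molars already have the condition that the aim says is to be prevented. For them, reaching ICDAS 4–6 is progression of an existing lesion; for a code 0 molar it means that a lesion has formed and then progressed. A code 3 molar is one code from the event and a sound molar is four.

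The background gives some reason to think that the contrast could differ between the two. It says of enamel lesions: "Remineralization with appropriate agents has proven effective to treat incipient carious lesions". It names fluoride as promoting this, and it describes sealants as a physical barrier. Varnish is repeated every 3 months, while the sealant is placed once without repair.

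What is at stake is the interpretation. A single pooled estimate, reported under the present aim, would be read as evidence about preventing caries in sound fissures, whatever mix of sound and carious molars produced it.

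**Working it through.** The documents give no figure for the share of study molars at ICDAS 1–3 or for progression by starting code, so there is no planned figure to reproduce. The sample size of 102 per group does not bear on this point. Everything below except the 102 is an assumption, used to show what is possible.

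**Inputs (assumed).** Share of molars with an enamel lesion at baseline, s = 20–40%. Risk of reaching ICDAS 4–6 under varnish: sound molars, a = 5–10%; lesion molars, b = 20–30%.

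**Step 1. Share of events from lesion molars** = s·b / [s·b + (1 − s)·a].

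| s | a | b | Calculation | Share |
|---|---|---|---|---|
| 20% | 10% | 20% | 0.04 / (0.04 + 0.08) | 33% |
| 20% | 10% | 30% | 0.06 / (0.06 + 0.08) | 43% |
| 20% | 5% | 20% | 0.04 / (0.04 + 0.04) | 50% |
| 30% | 5% | 30% | 0.09 / (0.09 + 0.035) | 72% |
| 40% | 10% | 30% | 0.12 / (0.12 + 0.06) | 67% |
| 40% | 5% | 30% | 0.12 / (0.12 + 0.03) | 80% |

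The range is 33–80%. Lesion molars supply a majority only when b/a exceeds (1 − s)/s, which is 4 at s = 20%, 2.33 at 30% and 1.5 at 40%.

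**Step 2. A pooled effect can hide prevention in sound molars.** Take s = 30%, a = 5%, b = 30%. Varnish risk = 0.7 × 0.05 + 0.3 × 0.30 = 0.125.
- Sealant halves the risk in sound molars and equals varnish in lesion molars: 0.7 × 0.025 + 0.3 × 0.30 = 0.1075. Pooled relative risk = 0.1075 / 0.125 = 0.86.
- Sealant halves the risk in sound molars and has relative risk 1.2 in lesion molars: 0.0175 + 0.108 = 0.1255. Pooled relative risk = 1.00.

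**Step 3. A pooled effect can mimic prevention in sound molars.** Take s = 40%, a = 10%, b = 30%. Varnish risk = 0.06 + 0.12 = 0.18. Sealant has no effect in sound molars and relative risk 0.55 in lesion molars: 0.06 + 0.066 = 0.126. Pooled relative risk = 0.126 / 0.18 = 0.70, an apparent 30% reduction with none in sound molars.

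**Step 4. How precise would the sound stratum be?** As a generous case, let all 102 children per group contribute four eligible molars: 408 molars, of which 70% are sound, about 286. At 5% risk that is about 14 events under varnish, and about 7 if sealant halves the risk. The standard error of the log relative risk is about √(1/14.28 + 1/7.14 − 2/285.6) = 0.45. The 95% interval around 0.50 is about 0.21 to 1.21, before any allowance for clustering within children.

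**The case against.** The strongest reply is that the design is coherent as it stands. The protocol twice defines its outcome as dentin caries, exclusion 5 removes molars that already have that event, and randomization protects the overall contrast. The introduction says that incipient lesions may progress to cavities, so stopping that progression is prevention of the defined outcome. This stands. A reader might infer that the aim goes unanswered; the documents do not support that, because the pooled comparison answers a clear question about dentin caries. What is missing is an aim worded to match it.

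A reader might also infer that the result will mostly reflect lesion arrest. The documents give no rates to support that, and under the assumptions above lesion molars may supply as little as a third of the events.

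Nor do the documents set a purely remineralizing varnish against a purely mechanical sealant. Section b) credits glass ionomer with fluoride release that helps to prevent caries. The actions overlap, so a different effect by baseline status is possible but not shown.

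Finally, it is tempting to rest the main conclusion on ICDAS 0 molars alone. Three things count against that:
- Events in that stratum may be few (Step 4).
- Code 1 is visible only after prolonged drying, while the examination describes wiping with gauze and cotton swab, so some code 1 molars may be recorded as sound.
- A sound molar must pass through the enamel stage to reach ICDAS 4–6, so even that stratum mixes onset with arrest of new lesions.

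These are good reasons to keep the pooled effect as primary. They do not justify leaving recorded baseline status out of the model, or leaving the aim broader than the design can support.

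**Conclusion.** The point holds as a limit on interpretation, not as a flaw in the validity of the comparison. The trial can estimate the effect on dentin caries in molars that are sound or have enamel lesions. As planned, it cannot say whether an effect reflects prevention in sound molars, arrest of existing lesions, or both. Under assumed values, lesion molars supply 33–80% of events. With relative risks that are also assumed, a halving of risk in sound molars could appear as a pooled relative risk of 0.86 or 1.00, and no effect in sound molars could appear as 0.70. These figures show that masking or mimicry is possible, not that it is likely. The change is worth making because it uses data already collected.

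**What to change.** 1. Restate the aim and hypothesis in section c) as prevention of dentin caries (ICDAS 4–6) on second primary molars that are sound or have enamel lesions.
2. In d)(iv), add baseline molar ICDAS (0 versus 1–3) as a covariate in the multi-level logistic model, with ICDAS 4–6 as its outcome. Keep the pooled treatment effect as primary, taken from the fit without the interaction.
3. In a second fit, add the treatment-by-baseline-ICDAS interaction. Report the sealant-versus-varnish effect with its interval in each stratum as a prespecified secondary analysis. Define strata by molar and retain the child-level random effect, since one child may contribute both sound and lesion molars.
4. State that no claim about preventing caries onset in sound molars will be drawn from the pooled result alone.

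The cost is a change of wording and additional model terms, with no new data, visits or change in eligibility. The downside is that the stratum estimates will be imprecise and the 0/1 boundary is open to misclassification. Both should be stated as limitations when the results are reported.

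### Does it matter that 102 children per group at 90% power cannot be rebuilt from the inputs the sample-size paragraph gives?

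*Combined protocol and SAP*

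**What the plan says.** Section d)(ii), Sample size calculation, names dentine caries (ICDAS 4 to 6) on the occlusal surfaces of primary second molars as the primary outcome. It sets a type I error of 0.05 and 90% power and cites a previous trial in primary molars in which "the real difference between fluoride varnish and sealant effect on occlusal caries reduction was 30" per cent. From this it states that "a minimum of 102 children in each group will be required", then enlarges each group by about a quarter for drop-out, to 128 per group and 256 in all.

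Three other places bear on the calculation:

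- The hypothesis in section c) is directional: "Greater reduction in occlusal caries in preschool children by glass ionomer fissure sealant compared to topical application of 5% sodium fluoride varnish". Section d)(iv) sets a 5% level for all tests without naming sides.
- Under Outcome measures: "The unit of randomization will be each individual participant, but not each tooth of the mouth".
- Section d)(iv): "Since more than one molar will be included from one child, GLIMMIX procedure will be used to adjust for the clustering effect".

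The documents give no expected incidence in either arm, no scale for the 30%, no formula, no number of molars per child and no intraclass correlation (ICC).

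**The concern.** A power calculation for a binary outcome needs two proportions, and here there is only a difference of unstated scale. The reading matters a great deal. Taken as 30 percentage points, 102 per group is far more than needed. Taken as a 30% relative reduction at low or moderate incidence, the trial would fall well short of 90% power, and a null result could be mistaken for good evidence that sealant and varnish perform alike.

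The relative reading reaches 102 only at about 73% incidence on varnish. That looks high beside the survey figure in section b), that "more than 50% of the preschool children had caries experience", and beside the first exclusion in section d)(i): "Children with the presence of caries of ICDAS code 3, 4, 5, or 6 on other primary teeth". Counting children while modelling molars also raises the question of a missing clustering allowance. Since 102 is the only basis for enrolling 256 children, the gap looks serious at first.

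**Working it through.** **Inputs from the plan:** 5% significance, 90% power, a 30% difference, 102 per group, about 25% added for drop-out. **Assumed, because the plan is silent:** every incidence below, the number of molars per child and the ICC.

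**The step that can be checked.** 102 × 1.25 = 127.5, rounded up to 128; 128 × 2 = 256. This agrees with the plan.

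**Formula (pooled two-proportion test).** With p̄ = (p1 + p2)/2,

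n per group = [z_α √(2p̄(1−p̄)) + z_β √(p1(1−p1) + p2(1−p2))]² / (p1 − p2)²,

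where z_β = 1.2816 and z_α = 1.960 two-sided or 1.645 one-sided.

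**Absolute 30 points.** The largest n is at 65% versus 35%: (1.960 × 0.7071 + 1.2816 × 0.6745)² / 0.30² = (1.3859 + 0.8645)² / 0.09 = 56.3, so 57 (63 with continuity correction). No base rate gives 102. The lowest power at 102 is 99.3%.

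**30% relative reduction.** n = 102 at about 72.8% versus 51% two-sided, or 67% versus 47% one-sided.

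Two-sided power at 102 is Φ{[(p1 − p2)√102 − 1.960 √(2p̄(1−p̄))] / √(p1(1−p1) + p2(1−p2))}. For 20% versus 14% this is Φ[(0.6060 − 1.960 × 0.5312) / 0.5295] = Φ(−0.82) = 21%. The other cases are:

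| Assumed varnish incidence, per child | Sealant incidence | Power at 102 | n per group for 90% |
|---|---|---|---|
| 10% | 7% | 12% | 1814 |
| 20% | 14% | 21% | 822 |
| 30% | 21% | 31% | 491 |
| 40% | 28% | 44% | 326 |
| 50% | 35% | 58% | 227 |

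**Other readings that give about 102 (two-sided).**

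- A 30-point difference in prevented fraction: 42% versus 21% needs 101. Here 21/0.30 implies a 70% untreated rate.
- A 1.3-fold ratio of caries-free children: 35% versus 15.5% needs 103. Here 84.5/65 = 1.3.

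**What 102 per group detects with about 90% power, per child, two-sided.** 50% versus 28%, 40% versus 19.5%, 30% versus 11.7%, or 20% versus 5.1%.

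**Clustering.** The count is in children and children are randomised, so a per-child comparison needs no tooth-level inflation. With m molars per child the effective number per group is 102m / [1 + (m−1)ICC]. For m = 4 and ICC 0.3 this is 408/1.9 = 214.7; at ICC = 1 it falls to 102 and no lower. At a given per-molar incidence, extra molars cannot take the trial below the information in 102 independent units. Per-molar incidence is a different quantity from the per-child incidence in the table, so power on the two scales should not be compared directly.

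**The case for a change.** The strongest case for a change is that the trial's central quantitative justification cannot be checked, and one reworded paragraph would cure it at no cost in enrolment. The cited trial does not fill the gap unaided: its title in the reference list describes one year of follow-up in children regularly receiving varnish, whereas this trial runs 24 months. Under the relative reading the shortfall at moderate incidence is large.

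What stands is that the inputs are absent and a reader of this document alone cannot recover them. The step from absent to wrong does not stand. The low power figures need a relative reading plus an incidence that no section supplies: 21% belongs to an assumed 20% incidence and is not a lower bound, since 10% gives 12%.

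The doubt about 73% is also inconclusive. It sets 24-month incidence in children selected for moderate to high risk against survey prevalence in all preschool children. Second molars are excluded only at ICDAS 4 to 6, and section b) says "second primary molars were reported to be the most susceptible to caries development". The exclusion for caries on other teeth pulls the other way, but does not rule the rate out.

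**Conclusion.** The 102 is undocumented, not shown to be wrong. Depending on the scale of the 30% and on incidences that must be assumed, two-sided per-child power at 102 runs from 12% (relative, 10% incidence) through 58% (relative, 50% incidence) to over 99% (absolute). The stated 90% lies inside that span and is met by several input pairs. The clustering strand shows no loss of power.

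The plan needs no change because nothing done in the trial depends on the missing detail. Stating the inputs would leave the 256 children, the randomisation by child and the molar-within-child model as they are. The open choices have sensible defaults: a two-sided test at 5%, and a treatment estimate with its confidence interval. A null result should be judged by that interval, which shows directly which differences remain compatible with the data, and not by the planned 90%. This conclusion rests on the pooled two-proportion approximation and on 102 evaluable children per group.
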